### 6.2.2.1 Adverse Event Definitions

An AE is defined as any untoward medical occurrence associated with the use of a drug in humans, whether or not considered drug related. Participants will be instructed to contact the investigator at any time after randomization if any symptoms develop.

A TEAE is defined as any event not present before exposure to study drug or any event already present that worsens in intensity or frequency after exposure. TEAE will be assessed from first dose of study drug until EOS and should be followed until they are resolved, stable, or judged by the investigator to be not clinically significant.

A suspected adverse reaction is any AE for which there is a reasonable possibility that the study drug caused the AE. For the purposes of investigational new drug safety reporting, “reasonable possibility” means that there is evidence to suggest a causal relationship between the study drug and the AE. A suspected adverse reaction implies a lesser degree of certainty about causality than an adverse reaction.

An AE or suspected adverse reaction is considered “unexpected” if it is not listed in the investigator brochure or if it occurs with specificity or severity that has not been previously observed with the study drug being tested; or, if an investigator brochure is not required or available, the AE or suspected adverse reaction is not consistent with the risk information described in the general investigational plan or elsewhere in the current application. For example, under this definition, hepatic necrosis would be unexpected (by virtue of greater severity) if the investigator brochure referred only to elevated hepatic enzymes or hepatitis. Similarly, cerebral thromboembolism and cerebral vasculitis would be unexpected (by virtue of greater specificity) if the investigator brochure listed only cerebral vascular accidents. “Unexpected,” as used in this definition, also refers to AEs or suspected adverse reactions that are mentioned in the investigator brochure as occurring with a class of drugs or as anticipated from the pharmacological properties of the drug but are not specifically mentioned as occurring with the particular drug under investigation.

An AE is considered an SAE/suspected unexpected serious adverse reaction if, in the view of either the investigator or sponsor, it results in any of the following outcomes:

- Death
- Life-threatening AE

- Inpatient hospitalization or prolongation of existing hospitalization

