#### **6.2.2.4 Assessment of Severity**

Seriousness (Section 6.2.2.1) and severity of an event are not synonymous. The severity (or intensity) of an AE refers to the extent to which it affects the participant's daily activities and will be classified as mild, moderate, or severe using the following criteria:

- Mild: These events require minimal or no treatment and do not interfere with the participant's daily activities.
- Moderate: These events result in a low level of inconvenience or require minor therapeutic measures. Moderate events may cause some interference with normal functioning.
- Severe: These events interrupt a participant's usual daily activity and may require systemic drug therapy or other treatment. Severe events are usually incapacitating.

Changes in the severity of an AE should be documented to allow the duration of the event at each level of intensity to be assessed. An AE characterized as intermittent does not require documentation of the onset and duration of each episode.

The Common Toxicity Criteria for Adverse Events (CTCAE) V5.0 grading criteria will also be used for assessment of severity of AEs.

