8.1. Adverse Events

An adverse event (AE) is defined as any untoward medical occurrence associated with the use of a drug in humans, whether or not considered drug related.

A treatment emergent AE (TEAE) is defined as any event not present before exposure to study drug or any event already present that worsens in severity or frequency after exposure.

An AE is considered a serious AE (SAE) if, in the view of either the investigator or sponsor, it results in any of the following outcomes:

- Death
- Life-threatening AE
- Inpatient hospitalization or prolongation of existing hospitalization
- Persistent or significant incapacity or substantial disruption of the ability to conduct normal life functions
- Congenital anomaly or birth defect

Important medical events that may not result in death, be life threatening, or require hospitalization may be considered serious when, based upon appropriate medical judgment, they may jeopardize the participant and may require medical or surgical intervention to prevent one of the outcomes listed in this definition.

The AE's relationship to study treatment will be evaluated by the investigator. The following relationships will be collected on eCRF: probably related, possibly related, or not related. The AEs that are evaluated as probably or possibly related will be considered treatment-related AEs for summary purpose.

The severity of AEs will be classified by the investigator as mild, moderate, or severe, and AEs will also be graded based on Common Toxicity Criteria for Adverse Events (CTCAE) V5.0.

Adverse events of special interest (AESIs) will be identified by the investigator on the eCRF. AESIs include:

- Grade ≥ 2 increased bilirubin
- Grade ≥ 2 increased alanine aminotransferase (ALT)
- Grade ≥ 2 increased aspartate aminotransferase (AST)

An overall AE summary will be generated presenting the frequency and percentage of participants and the number of AEs, by treatment and the overall population, for the following:

- (For Part A Only) Any AE (presented by overall only)
- Any TEAE
- Any TEAE related to Plixorafenib
- Any TEAE related to Cobicistat
- Any Grade ≥ 3 TEAE
- Any SAE
- Any TEAE leading to study drug discontinuation
- Any TEAE leading to early study discontinuation
- Any AESI
- Any Death

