All AEs will be coded using MedDRA (version to be delineated in the CSR). The TEAEs will also be summarized, by treatment and overall population, by system organ class (SOC), preferred term (PT), by CTCAE toxicity grade, and either:

- Part A: by Relationship to study treatment.
- Part B: or for related TEAEs only.

Treatment Emergent AESIs will also be presented by SOC and PT, by treatment and overall.

An additional table will summarize the TEAEs by treatment sequence and overall, by SOC and PT.

The TEAE summary tables will be sorted by SOC and PT. System organ class will be displayed alphabetically. Preferred term will be displayed in descending order of overall frequency and then alphabetically within SOC. A participant with 2 or more events within the same level of summarization will be counted only once in that level using the highest CTCAE grade, or most related incident (for Part A summary by relationship only). Percentages will be based on the number of participants in the safety set.

All AEs will be presented in a data listing. Separate data listings will be generated for treatment related AEs, AESIs, SAEs, and AEs leading to treatment discontinuation.

For Part A and B, a TEAE will be assigned to the last treatment received prior to the assessment/observation as below:

- Treatment received in Treatment Period 1 if the AE start date/time is on or after the first dose of study drug in the Treatment Period 1, but prior to the first dose of study drug in Treatment Period 2.
- Treatment received in Treatment Period 2 if the AE start date/time is on or after the first dose of study drug in the Treatment Period 2, but prior to the first dose of study drug in Treatment Period 3.
- Treatment received in Treatment Period 3 if the AE start date/time is on or after the first dose of study drug in the Treatment Period 3.

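### SAP 8.1 assigns TEAEs to treatment by AE start date alone, so an event that worsens after a dose may be counted under the earlier treatment or under no treatment

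*SAP*

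**What the plan says.** Three parts of SAP 8.1 bear on the point.

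- **Definition.** Besides new events, a TEAE includes "any event already present that worsens in severity or frequency after exposure". Protocol 6.2.2.1 has the same second limb: "any event already present that worsens in intensity or frequency after exposure".
- **Lead-in to the assignment rule.** "a TEAE will be assigned to the last treatment received prior to the assessment/observation as below".
- **Operative windows.** Period 1 applies "if the AE start date/time is on or after the first dose of study drug in the Treatment Period 1" and before the Period 2 dose. Period 2 is built in the same way. Period 3 applies "if the AE start date/time is on or after the first dose of study drug in the Treatment Period 3".

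The assignment feeds the by-treatment TEAE tables by SOC, preferred term and CTCAE grade, and the by-treatment AESI table. For counting, SAP 8.1 adds that someone with several events in one level "will be counted only once in that level using the highest CTCAE grade".

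On collection, Protocol 6.2.2 assesses AEs from signature of the consent form to EOS. Protocol 6.2.2.4 requires changes in severity to be documented so that time at each level can be assessed. Neither document says whether such a change becomes a new AE record with its own start date, or which grade a single record carries.

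**The concern.** The definition admits events because they worsen, and the lead-in points to the time of observation, but the windows look only at when the event began. These three statements do not agree, and a programmer who follows the windows will apply the start date.

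Safety by treatment is at stake, and safety is a primary objective of both parts. The known signal is hepatic: Protocol 1.3 describes transient rises in ALT, AST and bilirubin, and the AESIs are Grade 2 or higher rises in those tests. Suppose a Grade 1 ALT rise is recorded as an AE on Day 4 and found at Grade 2 on Day 11. It meets the AESI threshold only after the Period 2 dose, yet by start date it belongs to Period 1. In Part A sequence 1:3:2 that would place a worsening seen after plixorafenib plus cobicistat with food under plixorafenib alone.

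**Working it through.** The plan gives no figure that depends on this rule, so there is nothing to reproduce. The check applies the windows literally to hypothetical AEs and then counts participants per treatment.

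**Inputs.** Doses are on Days 1, 8 and 15 (SAP 3.1 and 3.2). AEs are collected from consent, and screening runs from Day -28 to Day -1. Planned numbers are 12 in Part A and 16 in Part B (SAP 4.1), with equal allocation to 6 and 4 sequences respectively.

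**Step 1: where each event falls.** The middle column assumes one record per AE that keeps its original start date. The last column assumes that the worsening carries its own date.

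| Hypothetical AE | Start-date windows | Date of worsening |
|---|---|---|
| Starts Day 3, worsens Day 5 | Period 1 | Period 1 |
| Starts Day 3, worsens Day 9 | Period 1 | Period 2 |
| Starts Day 10, worsens Day 16 | Period 2 | Period 3 |
| Starts Day -5 (after consent), worsens Day 2 | none | Period 1 |
| Starts Day -5 (after consent), worsens Day 9 | none | Period 2 |

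The two pre-dose cases are TEAEs by definition but satisfy none of the three windows. They count overall and in no treatment column. The second and third cases depend on the record structure: if each grade change is a separate dated record, the existing windows already give the last column.

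**Step 2: participants per treatment.** Part A is a complete crossover, so each treatment has 12 planned participants. In Part B (A:C:D, B:D:A, D:B:C, C:A:B) each treatment appears in 3 of 4 sequences. With 16/4 = 4 per sequence, that is 3 × 4 = 12 per treatment.

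**Step 3: effect of one participant.** 1/12 = 8.3 percentage points. SAP 8.1 bases percentages on the safety set; if that means all 16 in Part B, the effect is 1/16 = 6.3 points.

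**Step 4: which columns move.** A pre-dose-onset case changes one column, the one from which it is missing. When an event carries over a dose, splitting the record leaves the original onset in the earlier column at its own grade and adds the worsening to the later column. A high-grade row would change in both columns only if the single record carried its maximum grade under the earlier treatment.

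**The case against.** The strongest reply is that the harm depends on an eCRF convention that the documents do not show. Protocol 6.2.2.4 requires severity changes to be documented; if that is done as separate dated records, the windows place a worsening under the later treatment. This stands, and it makes the carried-over case conditional. It does not settle which structure is used, and a pre-dose onset that keeps its original start date still has no window.

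Other replies also narrow the point:

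- A reader might infer that a worsening is always charged to the earlier treatment at its peak grade. The documents do not support this. The highest-grade sentence deals with participants who have two or more events in the same level; it does not say what grade a single worsening event carries.
- A reader might infer that recurrences after later doses always stay with the first treatment, because "An AE characterized as intermittent does not require documentation of the onset and duration of each episode". That exemption covers only AEs characterised as intermittent. Nothing requires a resolved event that recurs after a later dose to be so characterised.
- Under Protocol 6.2.2.3, a condition present at screening is recorded as an AE when it deteriorates. The no-column case is therefore mainly an AE that arises after screening and before the first dose.
- Hepatic signals do not rest on AE tables alone. SAP 8.2 tabulates serum chemistry by treatment, including post-baseline extremes, and adds a summary against a pre-treatment baseline. This is partial protection: it does not correct the AESI and TEAE columns.
- A worsening after a later dose may be the earlier treatment's effect still evolving. Either rule can misattribute. But the SAP's definition and lead-in already point to the time of worsening, so the windows conflict with the plan's own stated principle.

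**Conclusion.** The concern holds in a limited form. The start-date windows conflict with the TEAE definition and the lead-in of the same section. For an AE with onset between consent and first dose that worsens after dosing, the gap follows from the text, provided that the record keeps its original start date. For an AE that worsens after a later dose, counting it under the earlier treatment is the natural reading but depends on how the eCRF stores grade changes.

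The effect is confined to by-treatment tables; overall counts and listings are unaffected. The size is 8.3 points per misassigned participant, or 6.3 in Part B with the whole safety set as denominator. This assumes that all planned participants are dosed as randomised, with 4 per sequence in Part B. The number of such events cannot be estimated from the documents. The change is worth making because by-treatment safety is a primary objective in both parts and the correction is cheap.

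**What to change.** Amend the three windows in SAP 8.1 so that each TEAE is assigned by its onset or, for an event that worsens after a dose, by the documented date of worsening, to the last treatment received before that date. Split the record in the analysis data at that date, so that grade tables use the grade reached within the assigned window. This also gives pre-dose-onset AEs a treatment column.

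The dates should exist, since Protocol 6.2.2.4 already asks for severity changes and also uses CTCAE grading for severity. For Part A, which SAP Section 10 says has already been analysed, apply the rule to the severity-change data already collected. Dropping the protocol's exemption for intermittent AEs is not needed. A worsening in frequency alone may then lack a date for such events, and the SAP should say how those are assigned.

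The cost is a short SAP amendment and slightly more AE analysis records. The downside is that an event still evolving from the earlier treatment may also be counted under the later one; a footnote to the by-treatment tables can say so.

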8.2. Clinical Laboratory Evaluations

The following laboratory tests will be performed for Part A and B:

Hematology	Absolute neutrophil count and differential, hematocrit, hemoglobin, mean corpuscular hemoglobin, mean corpuscular hemoglobin concentration, leukocytes-absolute counts and percentages (basophils, eosinophils, lymphocytes, monocytes, neutrophils), mean corpuscular volume, platelet count, red blood cell count, and red cell distribution width
Serum Chemistry	Alanine aminotransferase, albumin, alkaline phosphatase, aspartate aminotransferase, bilirubin (total + indirect and direct fractions), blood urea nitrogen, calcium, carbon dioxide, chloride, creatinine, gamma-glutamyl transferase, globulin, glucose, lactate dehydrogenase, phosphorus, potassium, sodium, total protein, uric acid, and creatine kinase
Urinalysis	Appearance, bilirubin, color, glucose, ketones, leukocytes, reflex microscopy (performed if dipstick is positive for protein or the blood value is 1+ or greater; and includes bacteria, casts, crystals, epithelial cells, red blood cells, and white blood cells), nitrites, occult blood, pH, protein, specific gravity, turbidity, and urobilinogen
Other tests	
Serology: Hepatitis B surface antigen, hepatitis C virus antibody, and human immunodeficiency virus antibody types 1 and 2 (screening only)
 
Urine drug screen (alcohol, amphetamines, barbiturates, benzodiazepines, cannabinoids, cocaine metabolites, cotinine, methamphetamines, methylenedioxymethamphetamine, and opiates [including heroin, codeine, and oxycodone])
 
Female participants: Follicle-stimulating hormone, urine pregnancy test/ serum pregnancy test (human chorionic gonadotropin)

The hematology, serum chemistry, and urinalysis tests will be performed at the timepoints indicated in the schedule of assessments (schedules of assessments can be found in [Section 13](#)).

All clinical laboratory test results will be presented in the data listings. Laboratory values that are outside of the normal reference range will be flagged in the data listings. Laboratory values will

also be graded per CTCAE V5.0, and the resulting grade for abnormal tests will be reported in the data listings.

Clinically significant laboratory test results and their associated adverse events or medical history, as recorded by the investigator on the laboratory eCRF, will be presented in a data listing.

Actual values and change from baseline for hematology and serum chemistry at each time point, and at the maximum and minimum post baseline value will be tabulated by treatment for the safety set.

An additional summary presenting the actual values and change from baseline for hematology and serum chemistry at each time point, and at the maximum and minimum post baseline value, using an alternate definition of baseline will be tabulated. For the summary, baseline will be defined as the last non-missing assessment (including repeat and unscheduled assessment) on or prior to Check-In (Day -1).

